9.5.2.1.4 Reporting Adverse Events and Serious Adverse Events

At each visit, patients are to be queried regarding any AEs or SAEs that have occurred since the previous visit. Patients will be asked to volunteer information with a nonleading question such as, “How do you feel since your last visit?” Study center personnel will record all pertinent information in the patient’s eCRF.

All AEs must be recorded on the appropriate AE reporting page of the patient’s eCRF whether or not they are considered causally related to the IP.

For every AE, the investigator must:

- Provide an assessment of the seriousness of the event (ie, is it an SAE?), as well as the severity and casual relationship
- Document all actions taken with regard to the IP
- Detail any other treatment measures taken for the AE
- Document the outcome of the AE

In addition, patients are to be reminded, as described in the ICF and in accordance with Section 9.5.2.1, to notify study center personnel of any AEs occurring during the 30-day posttreatment protocol period. Any AEs reported by the patient (or patient representative) during this period are to be recorded in original source documents. AEs are also to be recorded in the eCRF if at least one of the following conditions is met: 1) the event meets the criteria for an SAE (see Sections 9.5.2.1.3 and 9.5.2.1.4), and/or 2) the event is judged by the investigator to be potentially causally related to IP (Section 9.5.2.1.1).

Any AEs that are ongoing at the time of patient exit from the protocol will be followed until the condition returns to pre-treatment protocol status, has resolved or stabilized, or can be explained as being unrelated to the IP. If a follow-up visit is deemed necessary for appropriate safety surveillance, it will take place within 30 days of the last known dose of IP.

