9.5.2.2 Immediate Reporting of Serious Adverse Events

The sponsor is required to inform worldwide regulatory authorities of SAEs that meet specific criteria. Therefore, the sponsor must be notified immediately regarding any SAE that occurs after informed consent is obtained.

Within 24 hours of learning of any AE that meets one of the criteria for an SAE, the study center personnel must report the event to Global Drug Safety on the SAE Form for Clinical Trials. The Study Physician may also be notified by telephone.

If, during follow-up, any nonserious AE worsens and eventually meets the criteria for an SAE, that AE should be recorded as a new SAE.

The study center must transmit the SAE Form for Clinical Trials to the SAE email address or fax number shown below. Even if an initial report is made by telephone, the SAE Form for Clinical Trials completed with all available details must still be emailed or faxed within 24 hours of knowledge of the event at the study center.

Supplemental information should be submitted as soon as available and may include laboratory results, radiology reports, progress notes, hospital admission and emergency room notes, holding and observation notes, discharge summaries, autopsy reports, and death certificates.

The investigator is expected to take all therapeutic measures necessary for resolution of the SAE. Any medications or procedures necessary for treatment of the SAE must be recorded on the appropriate pages of the patient’s eCRF. All SAEs are to be followed by the study center staff until resolution or until the SAE is deemed stable. ***The sponsor may contact the study center to solicit additional information or follow up on the event.***

[Redacted]

[Redacted]

[Redacted]

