9.7.6.1 Adverse Events

AEs will be coded by system organ class (SOC) and preferred term using the *Medical Dictionary for Regulatory Activities*.

An AE (classified by preferred term) that occurs during the OLTP or thereafter will be considered a treatment-emergent adverse event (TEAE) if it was not present before the date of the first dose of IP in the OLTP or was present before the first dose of IP of the first lead-in study and increased in severity during the OLTP or thereafter. If more than 1 AE is reported before the date of the first dose of IP in the OLTP and coded to the same preferred term, the AE with the greatest severity will be used as the benchmark for comparison with the AEs occurring during the OLTP that were also coded to that preferred term.

The number and percentage of patients reporting TEAEs during the OLTP will be tabulated by SOC, preferred term, and further categorized by severity and causal relationship to the IP. If more than 1 AE is coded to the same preferred term for the same patient during the OLTP, the patient will be counted only once for that preferred term using the most severe and most related occurrence for the summarization by severity and by causal relationship to the IP.

The incidence of common ($\geq 2\%$ of patients) TEAEs during the OLTP will be summarized by preferred term and will be sorted by decreasing frequency.

An SAE that occurred between the date of the first dose of the IP and 30 days after the date of the last dose of IP, inclusive, will be considered an on-therapy SAE. The number and percentage of patients who had on-therapy SAEs during the OLTP will be summarized by preferred term and sorted by decreasing frequency.

The number and percentage of patients who had fatal on-therapy SAEs during the OLTP will be summarized by preferred term and sorted by decreasing frequency.

The incidence of TEAEs leading to premature discontinuation of IP during the OLTP will be summarized by preferred term and will be sorted by decreasing frequency.

Listings will be presented for all patients with SAEs, patients with AEs leading to discontinuation, and patients who died (if any).

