11.1 ADVERSE EVENTS

AEs will be coded using the *Medical Dictionary for Regulatory Activities (MedDRA)*.

An AE (classified by preferred term) that occurs during the OLTP will be considered a treatment-emergent adverse event (TEAE) if it was not present before the date of the first dose of IP in the OLTP or was present before the first dose of IP of the first lead-in study and increased in severity during the OLTP. If more than 1 AE is reported before the date of the first dose of IP in the OLTP and coded to the same preferred term, the AE with the greatest severity will be used as the benchmark for comparison with the AEs occurring during the OLTP that were also coded to that preferred term. An AE that occurred more than 30 days after the date of the last dose of open-label IP will not be counted as a TEAE. An AE that becomes serious during the OLTP will also be considered as TEAE.

The incidence of common (in $\geq 2\%$ of participants) TEAEs during the OLTP will be summarized by preferred term and will be sorted by decreasing frequency.

An SAE that occurred between the date of the first dose of the open-label IP and 30 days after the date of the last dose of IP, inclusive, will be considered a treatment-emergent SAE (TESAE).

The incidence of death, TEAE, treatment-related TEAE, TESAE, TEAEs leading to premature discontinuation of IP during the OLTP will be summarized.

Listings will be presented for all participants with SAEs, participants with AEs leading to discontinuation, and participants who died (if any).

12.0 **HEALTH ECONOMICS AND OUTCOMES ANALYSES**

Not applicable.

13.0 **INTERIM ANALYSIS**

No interim analysis is planned for this treatment protocol.

14.0 **DETERMINATION OF SAMPLE SIZE**

Not applicable.

15.0 **COMPUTER METHODS**

Statistical analyses will be performed using [REDACTED]

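### SAP 11.1 defines a treatment-emergent SAE by date alone, so the TESAE row is not guaranteed to sit inside the TEAE row

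*SAP*

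**What the plan says.** SAP 11.1 contains two separate rules.

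- **TEAE.** An AE, classified by preferred term, qualifies "if it was not present before the date of the first dose of IP in the OLTP or was present before the first dose of". The second limb, cut short here, refers to treatment in the earliest lead-in study and also needs a rise in severity in the OLTP. Two sentences modify this. One sets an upper limit: "An AE that occurred more than 30 days after the date of the last dose of open-label IP will not be counted as a TEAE". The other adds a route in: "An AE that becomes serious during the OLTP will also be considered as TEAE".
- **TESAE.** The rule is a date window: "An SAE that occurred between the date of the first dose of the open-label IP and 30 days after the date" on which dosing ended, inclusive. No term history, severity comparison or reference to TEAE status is attached.

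Both rules feed one summary: "The incidence of death, TEAE, treatment-related TEAE, TESAE, TEAEs leading to premature discontinuation of IP during the OLTP will be summarized".

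Protocol 9.7.6.1 uses essentially the same date window, but an SAE inside it "will be considered an on-therapy SAE". The protocol does not call it treatment-emergent. SAP 17.0 uses the new label when it cancels the TESAE summary by preferred term, but does not list the relabelling as a change.

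On recording, Protocol 9.5.2.2 has this rule for events that escalate in follow-up: "any nonserious AE worsens and eventually meets the criteria for an SAE, that AE should be recorded as a new SAE".

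**The concern.** A reader of the summary will take the TESAE row to be the serious part of the TEAE row. The SAP's rules do not ensure that. A participant can have an SAE that counts as treatment-emergent while the same event fails the SAP's own test for a treatment-emergent AE. If no other event qualifies, that participant is absent from the TEAE row. If the SAE ended treatment, it is also absent from the row for TEAEs leading to discontinuation.

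This matters because SAP 17.0 cuts the AE reporting down to a few aggregate rows, the common-TEAE table and listings. Two of those rows could be understated, and the table could look internally inconsistent with no footnote to explain it.

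A second, related gap is the word *occurred*. The SAP does not say whether it means the onset of the AE or the date a seriousness criterion was first met. Two programmers could reach different TESAE counts from the same data.

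**Working it through.** The plan states no figure to reproduce, and sample size is not applicable in either document. The check is therefore one of logic: apply the SAP 11.1 rules literally to every combination of the features they use.

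**Inputs (SAP 11.1 unless noted)**

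- Earlier history of the preferred term: none; present before the first lead-in dose; or arising after that but before the first OLTP dose.
- Severity against the earlier event: same or higher.
- Earlier event: nonserious or serious.
- SAE date: in the OLTP, or in the 30 days after the last dose.
- An AE that turns serious is dated by its new SAE record (Protocol 9.5.2.2).

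**Number of in-window patterns.** With no earlier history there are 2 (serious from the start, or nonserious on treatment and later serious). With earlier history there are 2 origins × 2 severities × 2 seriousness states = 8. Each can fall in either period, so (2 + 8) × 2 = 20. All 20 are TESAEs.

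**Which of them are also TEAEs?** The last column takes *during the OLTP* literally for the severity limb and the becomes-serious clause.

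| Earlier history of the term | Severity | Earlier event | SAE in OLTP | SAE in 30 days after last dose |
|---|---|---|---|---|
| None (2 patterns) | – | – | TEAE | TEAE |
| Before lead-in | same | nonserious | TEAE (clause) | not TEAE |
| Before lead-in | same | serious | not TEAE | not TEAE |
| Before lead-in | higher | nonserious | TEAE | not TEAE |
| Before lead-in | higher | serious | TEAE (severity) | not TEAE |
| During lead-in | same | nonserious | TEAE (clause) | not TEAE |
| During lead-in | same | serious | not TEAE | not TEAE |
| During lead-in | higher | nonserious | TEAE (clause) | not TEAE |
| During lead-in | higher | serious | not TEAE | not TEAE |

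**Results**

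1. Literal reading: 3 of 10 OLTP patterns and 8 of 10 post-dose patterns are TESAEs but not TEAEs. 3 + 8 = 11 of 20.
2. Generous reading, with the 30 post-dose days treated as OLTP: the last column then matches the one before it, giving 3 + 3 = 6 of 20.
3. Without the becomes-serious clause, the three OLTP patterns marked (clause) would also fail: 11 + 3 = 14 of 20. The clause already closes part of the gap.
4. SAE dated after the 30-day limit: no pattern is a TESAE, so none can break nesting.

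The three OLTP failures all involve a term that was already serious before the first OLTP dose. One of them arose in the lead-in and worsened later, so it meets neither TEAE limb: it was present before the first OLTP dose, but not before the first lead-in dose.

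**Effect of the proposed fix on the literal reading.** Extending the becomes-serious clause to the end of the window rescues the 4 post-dose patterns with a nonserious earlier event: 11 − 4 = 7. Counting every TESAE as a TEAE removes the other 7, leaving 0 of 20.

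**Reading choices**

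- *Present before* is taken at preferred-term level, as any earlier report of that term. The SAP's benchmark sentence points that way.
- A new term in the 30 post-dose days is counted as a TEAE, because the 30-day cut-off implies it.

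**The case against.** The strongest reply is that the gap is small and partly closed by the SAP itself. A pre-existing nonserious AE that leads to hospitalization during the OLTP is a TEAE through the becomes-serious clause, so the commonest-looking example does not fail. That stands, and it is why the point is confined to terms already serious beforehand and to seriousness first arising in the 30 post-dose days. The generous reading of those 30 days is also plausible, since the TEAE cut-off runs to the same day. It still leaves 6 of 20 patterns. The literal reading has textual support too: Protocol 9.7.6.1 lets severity increase during the OLTP or later, and SAP 11.1 drops the later part.

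It can also be said that an SAE that ends treatment would ordinarily arise during the OLTP, where the clause applies. That largely holds if the OLTP runs past the last dose. However, doses may be up to 4 weeks apart, so such an SAE may well follow the last dose actually given. The unredacted text gives no date on which a participant's OLTP ends.

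A reader might infer something stronger: that an on-treatment AE turning serious after day 30 is lost, or that it breaks nesting. AEs still open at exit are indeed followed without a stated time limit ("Any AEs that are ongoing at the time of patient exit from the protocol will be followed until" resolution, stabilization or explanation). The documents nevertheless do not support that inference:

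- Such an event remains a TEAE through its original record and is simply not a TESAE, which is consistent with a subset.
- The 30-day limit is the protocol's own on-therapy window, so applying it is design rather than omission.
- If *occurred* means AE onset, the event is counted after all.
- SAP 11.1 lists all participants with SAEs with no date limit, so the event stays visible.

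Nor is there a case for extending TESAE beyond 30 days on this ground. That would depart from the protocol's window.

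**Conclusion.** The point holds in a narrow form. SAP 11.1 applies a treatment-emergent label to a date-only rule, and nesting of the TESAE row in the TEAE row is not guaranteed. The affected cases are chiefly a recurrence, as an SAE, of a term already serious before the first OLTP dose that meets no TEAE limb and, read literally, a pre-existing AE that first turns serious in the 30 days after the last dose.

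The pattern counts, 11 of 20 or 6 of 20 depending on the reading, show that the gap exists. They say nothing about how often it will occur. The documents give no SAE or recurrence rates, so no participant count is offered. At participant level the effect on the TEAE row is smaller still, because anyone with another qualifying TEAE is already counted there. The direction is known: the TEAE and TEAE-discontinuation rows can only be understated relative to TESAE.

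The second affected case depends on dating an escalated AE by its new SAE record. If *occurred* means original onset, that case drops out of TESAE. The first case remains on either dating, because a recurrence has its own onset. This is an inconsistency between stated rules in a descriptive, uncontrolled protocol. It threatens no hypothesis test, but it affects some of the few aggregate safety results that will be reported.

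**What to change.** Keep the protocol's window of last dose plus 30 days, and amend the SAP as follows:

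1. In SAP 11.1, extend the becomes-serious clause so that it runs from the first open-label dose to 30 days after the last dose.
2. Within the TEAE definition itself, add: *Every TESAE is also counted as a TEAE.* Placing it there means it amends the TEAE rule rather than contradicting it.
3. State whether *occurred* means AE onset or the date a seriousness criterion was first met, and how a new SAE record made under Protocol 9.5.2.2 is dated. Nesting holds on either choice once item 2 is in place, but the TESAE count may differ, so the choice should be fixed in advance.
4. In SAP 17.0, list the change from on-therapy SAE to TESAE and the added counting rule.

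The cost is a few sentences and one derivation rule setting the TEAE flag for every TESAE. Item 3 may also need a check of which dates the eCRF holds, since the documents do not show this. The downside is a possible slight rise in the TEAE percentages, including TEAEs leading to discontinuation.

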16.0 STATISTICAL AND DATA HANDLING CONVENTIONS**16.1 SUMMARY STATISTICS**

The following statistical summaries will be presented for each type of data:

- Continuous variables will be summarized by descriptive statistics (number of participants, mean, standard deviation [SD], median, minimum, and maximum values).
- Categorical variables will be summarized by frequency distributions (counts and percentages).

16.2 VISIT TIME WINDOWS

Not applicable.

16.3 DERIVED EFFICACY AND SAFETY VARIABLES

Not applicable.

16.4 REPEATED OR UNSCHEDULED ASSESSMENTS OF SAFETY PARAMETERS

Not applicable.

16.5 MISSING SEVERITY ASSESSMENT FOR ADVERSE EVENTS

If the severity is missing for an AE that started on or after the date of the first dose of the open-label IP, then a severity of *severe* will be assigned. The imputed values for severity assessment will be used for the incidence summary; the values will be shown as missing in the data listings.

16.6 MISSING RELATIONSHIP TO INVESTIGATIONAL PRODUCT FOR ADVERSE EVENTS

If the relationship to the IP is missing for an AE that started on or after the date of the first dose of the open-label IP, a causality of *yes* will be assigned. The imputed values for relationship to the open-label treatment will be used for incidence summary; the values will be shown as missing in the data listings.

16.7 MISSING DATE INFORMATION FOR ADVERSE EVENTS

The following imputation rules only apply to cases in which the start date for an AE is incomplete (ie, partly missing).

Missing month and day

- If the year of the incomplete start date is the same as the year of the first dose of open-label IP, the month and day of the first dose of open-label IP will be assigned to the missing fields.
- If the year of the incomplete start date is before the year of the first dose of open-label IP, *31 Dec* will be assigned to the missing fields.
- If the year of the incomplete start date is after the year of the first dose of open-label IP, *01 Jan* will be assigned to the missing fields.

Missing month only

- If only the month is missing, the day will be treated as missing and both the month and the day will be replaced according to the above procedure.

Missing day only

- If the month and year of the incomplete start date are the same as the month and year of the first dose of open-label IP, the day of the first dose of open-label IP will be assigned to the missing day.
- If either the year of the incomplete start date is before the year of the date of the first dose of open-label IP or if both years are the same but the month of the incomplete start date is before the month of the date of the first dose of open-label IP, the last day of the month will be assigned to the missing day.
- If either the year of the incomplete start date is after the year of the date of the first dose of open-label IP or if both years are the same but the month of the incomplete start date is after the month of the date of the first dose of open-label IP, the first day of the month will be assigned to the missing day.

If the stop date is complete and the imputed start date as above is after the stop date, the start date will be imputed by the stop date.

If the start date is completely missing and the stop date is complete, the following algorithm will be used to impute the start date:

- If the stop date is after the date of the first dose of open-label IP, the date of the first dose of open-label IP will be assigned to the missing start date.
- If the stop date is before the date of the first dose of open-label IP, the stop date will be assigned to the missing start date.

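### SAP 16.7 can turn an AE that ended before open-label dosing into a TEAE when its stop date is partial, and gives some AEs with no start date no date at all

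*SAP*

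**What the plan says.** SAP 16.7 opens by limiting itself: "The following imputation rules only apply to cases in which the start date for an AE is incomplete (ie, partly missing"). Its rules then run as follows.

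- **Month and day missing, same year as the first open-label dose:** "the month and day of the first dose of open-label IP will be assigned to the missing fields".
- **Day missing, same month and year as the first dose:** "the day of the first dose of open-label IP will be assigned to the missing day".
- **Earlier year or earlier month:** the last day of that year or month, so the AE stays before the first dose.
- **Correction against the stop date:** it applies "If the stop date is complete and the imputed start date as above is after the stop date", and the start then becomes the stop date.
- **Start completely missing:** "If the start date is completely missing and the stop date is complete, the following algorithm will be used to impute the start date". One branch covers a stop after the first dose (start set to the first-dose date). The other covers a stop before it (start set to the stop date).

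No rule in the SAP imputes a partial AE stop date; SAP 16.8 and 16.8.2 do so for medications only. SAP 11.1 makes an AE treatment-emergent if it was not present before the first open-label dose, and defines a treatment-emergent SAE by a window that opens on that date. The worst-case rules of 16.5 and 16.6 also depend on the start date; 16.5 begins "If the severity is missing for an AE that started on or after the date of the first dose of the open-label IP".

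**The concern.** AEs are the only safety parameter (SAP 11.0), and their status turns on the start date. Two things follow from the rules as written.

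First, the check that stops an imputed start from falling after the known end does not operate when the end is known only to the month or year. An event that the record itself shows was over can be placed on the first day of open-label treatment. It then counts as a TEAE and also leaves the pre-dose set that SAP 11.1 uses as its severity benchmark.

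Second, an AE with no start date that stopped one day after the first dose is assigned the first-dose date, while one that has not stopped is assigned nothing. Protocol 9.5.2.1.4 expects ongoing AEs. Without a date, neither the TEAE definition nor the triggers of 16.5 and 16.6 can be evaluated.

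Pre-dose records are foreseeable. SAP 11.1 compares open-label AEs with those reported before the first open-label dose, so lead-in AEs must be in the analysis data. Three of the four lead-in studies must have ended within about one month of Visit 1 (Protocol 9.3.1), so a lead-in AE in the same calendar year as the first dose is ordinary.

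**Working it through.** The plan has no figure to reproduce here. The check is to apply 16.7 literally. The first-dose date, 10 Sep 2018, is an assumption.

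**Worked cases**

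| Recorded start | Recorded stop | Start under 16.7 | Result |
|---|---|---|---|
| 2018 | Mar 2018 | 10 Sep 2018 | TEAE, though over by 31 Mar 2018 |
| 2018 | 20 Mar 2018 | 20 Mar 2018 | pre-dose; the correction works |
| 2017 | Mar 2018 | 31 Dec 2017 | pre-dose |
| Aug 2018 | Aug 2018 | 31 Aug 2018 | pre-dose |
| Sep 2018 | Sep 2018 | 10 Sep 2018 | TEAE; record cannot show when it ended relative to the dose |
| missing | 11 Sep 2018 | 10 Sep 2018 | TEAE |
| missing | 9 Sep 2018 | 9 Sep 2018 | pre-dose |
| missing | 10 Sep 2018 | none | undefined |
| missing | ongoing | none | undefined |
| missing | Mar 2018 | none | undefined |

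First row: from 31 Mar to 10 Sep is 30 + 31 + 30 + 31 + 31 + 10 = 163 days between the latest possible end and the imputed start.

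**Enumeration.** True start days ran from 1 Jul 2017 over 730 days, each with 15 durations between 0 and 180 days. Of these AEs, 5953 truly ended before the first dose. The number that 16.7 moves to the first-dose day depends on what is missing:

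| Start missing | Stop complete | Stop known to month | Stop known to year |
|---|---|---|---|
| month and day | 0 | 3193 | 3193 |
| day only | 0 | 36 | 36 |

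In no pattern was an AE that began on or after the first dose imputed to before it.

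Not all of these moves are avoidable. With start month and day missing and the stop known to the month, the stop month itself ends before the first dose in 3058 of the 3193; the other 3193 − 3058 = 135 ended in September 2018 and are ambiguous. When only the start day is missing, all 36 have a stop recorded as Sep 2018 or as 2018, so the record cannot place the end before the dose. The same holds for all 3193 with a stop known only as 2018. The rule contradicts the record itself where the stop month closes before the first dose.

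These counts weight every start day and duration equally. They show the mechanism and say nothing about how often it occurs.

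**The case against.** The best defence is that these are edge cases in a descriptive, single-arm access protocol, and that the one shown error runs in the conservative direction that 16.5 and 16.6 choose deliberately. AEs are queried at every visit (Protocol 9.5.2.1.4), visits are at most four weeks apart, and edit checks cover completeness (Protocol 9.6.2). Collection under this protocol starts at consent, which may share a visit with the first dose, so the false TEAE depends mainly on lead-in records whose date cleaning cannot be seen here. The preferred-term summary that SAP 17.0 retains has a 2% threshold; 0.02 × 1800 = 36 participants at full planned enrolment, so a few misdated records would seldom change it. All of this stands, and it limits the importance of the point.

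A reader might infer more than the documents support:

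- **That every AE with two partial dates is moved.** A partial start in an earlier year or month stays pre-dose.
- **That TEAE status is wrong in both directions.** No under-count was found. The undated AEs have undefined status; losing them would require the program to treat a missing start as not emergent, which the SAP does not say.
- **That undated AEs vanish from the report.** The SAP 11.1 listings of SAEs, AEs leading to discontinuation and deaths carry no start-date condition.
- **That a number of affected records can be given.** The documents contain neither AE counts per patient nor a rate of partial dates.

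Conservatism does not excuse the first defect. Worst-case imputation fills in what is unknown; here the rule overrides a stop month that is known.

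**Conclusion.** The point holds in limited form. SAP 16.7 can re-date an AE that ended before open-label treatment to the first-dose day when the stop date is partial and the partial start shares the first dose's year, or its month and year. Where the recorded stop period closes before the first dose, the result is plainly wrong (163 days in the example); in the remaining cases it is a conservative default for data that cannot settle the question. Section 16.7 also leaves TEAE status undefined when the start is completely missing and the AE is ongoing, has a partial stop date, or stopped on the first-dose day. Its scope sentence conflicts with its own rule for completely missing starts.

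The conclusion assumes that lead-in AEs enter the analysis data with partial dates intact and that 16.7 is programmed as written. It is worth correcting because the rule gives a wrong answer, even though few records are likely to be affected.

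**What to change.** Amend the scope sentence of 16.7 to cover completely missing as well as partly missing start dates. Replace the stop-date correction and the missing-start algorithm with:

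> Define the latest possible stop date as the complete stop date or, if partial, the last day of the known month or year. If the imputed start date is after the latest possible stop date, the start date is set to the latest possible stop date. If the start date is completely missing: when the latest possible stop date is before the first open-label dose, assign the latest possible stop date; otherwise (stop on or after the first-dose date, or no stop date), assign the first-dose date, except that an AE already recorded as present before the first open-label dose stays pre-dose.

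In the worked cases, a start of 2018 with a stop of Mar 2018 becomes 31 Mar 2018. With a missing start, the ongoing AE and the AE that stopped on 10 Sep 2018 receive 10 Sep 2018 (unless already recorded pre-dose), and the AE with stop Mar 2018 receives 31 Mar 2018. For starts with month and day missing and a stop known to the month, the enumerated moves fall from 3193 to the 135 ambiguous ones. Patterns in which the record cannot place the end before the dose keep the present default.

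The medication rules should not be copied across: when an imputed stop precedes the start, SAP 16.8 moves the start and SAP 16.8.2 moves the stop.

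The cost is a few lines of SAP text and one derivation step. No new data are needed.
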